#### **8.2.1 Completing the Audio Computer Assisted Self-Interview**

- The participant is reminded of his or her right to discontinue at any time with no penalty and the right to choose to leave any questions unanswered;
- The participant is given headphones and a iPad in an accommodating, private and quiet area;
- The research staff assists with ACASI tutorials; and
- If the participant requires a break, research staff will make sure the computer program is exited and re-entered properly so that the participant's privacy is maintained

#### **8.2.1 Debriefing and Referral Procedures for Audio Computer Assisted Self-Interview Participants**

- The participant will be debriefed about possible reactions to answering questions of a sensitive nature, such as short-term feelings of sadness or anxiety. Participants will be instructed to contact study personnel or to consult the list of referrals provided if feelings persist or worsen after several days;
- Referrals for mental health services will be provided to all participants, if warranted; and
- At the completion of the ACASI, the research staff member present during the session will ask the following question: *“Is there anything else about the interview that you would like to discuss?”*

If the respondent says “no,” they should be thanked for participation. The respondent will be given contact information for mental health personnel available at UC and informed that they can also contact study personnel in the event that issues or concerns arise later.

If the response indicates the participant is in urgent need of mental health assistance, site staff should follow their individual site procedures for acute mental health referrals. Site staff should contact a supervisor immediately and stay with the study participant until the supervisor, mental health professional or emergency services, if needed, arrives. Otherwise, the interviewer should say, *“If you decide that you would like to speak with a counselor, here is the contact information for a counselor and a list of agencies in the community that provide this service”* and provide the list of referrals.

### 8.3 Compensation

**Focus Groups:** Participants will receive \$40 each for focus group participation.

**Key Informant Interviews:** LGBTQ-friendly employers will be offered a \$10 gift card for key informant interview participation. All other participants will receive \$40 for key informant interview participation.

**CAB:** \$30 per meeting.

**Intervention Pre-Test:** Participants will receive \$30 for completing visit surveys at T1 and T2, \$40 for providing optional biologic specimens at T1, and \$20 per workshop session attended, for a possible total of \$180.

**Intervention Pilot:** Participants will receive \$30 for completing visit surveys at each time point, \$40 for providing optional biologic specimens at T1 and T3, \$40 per workshop session attended, for a possible total of \$330.

**Intervention Community Pilot:** Participants will receive \$30 for completing visit surveys at each time point, \$40 for providing optional biologic specimens at T1 and T3, and \$30 per workshop session attended, for a possible total of \$290.

### 8.4 Intervening on “Social Harms”

#### 8.4.1 Potential risks

Potential risks consist of participants being uncomfortable or emotionally upset as a result of the questions asked in the assessments, and potential breaches of confidentiality. However, participants are allowed to discontinue the study at any time and to not respond to questions they are uncomfortable with, without any penalty. All information disclosed to the research team will remain confidential, even if a participant chooses to withdraw from the study. Additionally, study participants can ask study staff to provide any needed referrals to counselors or other support if they become emotionally upset. Study participants will also have access to a clinician or social worker who can help them address any feelings and/or questions which arise over the course of their participation. The investigative team has conducted studies with hundreds of assessment visits and has managed all visits successfully. Procedures for youth who do experience discomfort are detailed below.

All study records that identify the participant will be kept confidential, however there is a risk of loss of confidentiality such as by mandated reporting of child abuse/neglect for participants 16-17 years old. All healthcare professionals are required by law to report suspected cases of abuse and/or neglect. Although several of the proposed assessment measures include elicit information about experiences of discrimination and sexual behaviors, they do not specifically address child abuse or neglect. Thus, a report of abuse or neglect will only occur if the participant knowingly volunteers this information. In addition,

all participants are told in the consent process that statements of potential harm-to-self or others may require further assessment and/or reporting. The research team has specific procedures in place for referrals and strict confidentiality reporting.

Additionally, a potential risk to confidentiality may occur if a participant tests positive for HIV or an STI during the course of the study. All participants will be told of reporting requirements during the consent process. If a participant tests positive for HIV or an STI, s/he will be referred to the Chicago Center for HIV Elimination (CCHE) for confirmatory HIV testing and appropriate care. CCHE is required to report all new cases of HIV by name and contact information to the Illinois Department of Public Health. Other information, including risk factors and sex contacts, are also requested for partner services. As an additional safeguard, the proposed study has two practicing physicians who have extensive experience treating STIs and HIV/AIDS among YMSM and YTW of color.

There is a general potential risk of a breach in confidentiality of participant information. However, all investigators and study staff have been involved in several local and national studies of YMSM and YTW and have considerable experience implementing measures to protect participant confidentiality. Some of these steps include signed confidentiality agreements, in-service training on confidentiality, and the assignment of study ID numbers for all participants. Additionally, all front-line research staff who will be working with the participants throughout the project will undergo routine ethics training and complete specialized confidentiality training around HIV and other sensitive issues through the Chicago Department of Public Health. All staff will have completed training regarding HIV prevention and PrEP access through the AIDS Foundation of Chicago's (AFC) "*Ready Set PrEP!*" should participants request additional information on these services. All staff will complete the Midwest AIDS Training and Education (MATEC) training and CDC Passport to Partner Services HIV and STI Prevention training prior to implementation. All data will be collected on secure network hosted by the university technology services.

#### 8.4.2 Potential coercion

Any study that pays a stipend may produce coercion. Eliminating the possibility of coercion by not awarding stipends would make it impossible to conduct many studies, and would shortchange subjects who provide time and energy, and may incur costs such as bus, train or cab fares. The resolution to this problem is to ensure that stipends are not inappropriately large, to probe potential subjects to make sure they have not been coerced, and to give persons who may have been coerced the opportunity not to enroll in the study in a manner that will protect them from retribution by the person coercing them. We believe we meet these conditions. The employment program session stipends proposed are similar to other studies used by members of the investigative team, and have not raised issues of coerciveness.

#### 8.4.3 Protection against risk

##### 8.4.3.1 Discomfort or distress during the research

Because there is a potential for discomfort or distress due to the research topic, we will make every effort to create a secure environment (ensuring privacy) prior to conducting baseline and follow-up assessments and intervention sessions. Participants will be told that they do not have to answer any question they do not wish to. Participants experiencing mild distress during the assessments will be offered a small break or will be rescheduled to complete the assessment at a later date. In the unlikely event that a participant experiences considerable distress, we will make a referral (if needed) for clinical assessment and/or counseling provided at each of the primary sites. Participants will be given the names and office phone numbers of the assessor, the Site Lead, and the Project Coordinator, and will be provided with referrals for mental health and support services. The Site Lead will be on-call for any serious problems that arise during assessments and intervention sessions.

#### 8.4.3.2 Disclosure of abuse, homicide or suicide risk

A number of procedures will be taken to minimize risk to participants. The consent procedures will explicitly state that participation in the research is voluntary, and that questionnaires will include items about sexual history, substance use, and sexual risk behaviors. Participants will be informed of the confidentiality of their responses as well as the limits of that confidentiality. If a participant discloses suicidal ideation, any type of violence, or homicidal intent, the research team will assess the level of risk and determine the best course of action (e.g., sending the participant to the emergency room, notifying the police). Youth under age 18 will be informed that disclosure of violence or victimization relating to a family member will require an evaluation by onsite behavioral health staff to determine the best course of action, and that under conditions of immediate danger or harm may require reporting or notification to appropriate authorities (i.e. the police or the Department of Children and Family Services). A determination of the decision-making capacity of the participants will be done prior to obtaining consent and research staff will pay particular attention to participants' understanding of the risks associated with disclosure of information and the implications of that disclosure in accordance with state law.

During all study visits, there will be an on-site behavioral health clinician or social worker to provide clinical backup to the RA, particularly concerning issues of child abuse, neglect, and suicidality. The on-site behavioral health staff will have specific clinical expertise in managing the unique challenges facing young sexual and gender minorities. Consistent with abuse and/or neglect reporting requirements, should a report to the authorities be required, the information provided will be from the Project Lead at each site. No mention of the youth's participation in this particular research project will be disclosed. We will inform participants that criminal behavior (i.e. drug use) is not reported to authorities and that the information is entirely confidential. These procedures will be reviewed in writing and in person by the RA as part of the informed consent process to help youth assess whether they wish to participate in the research, and to minimize the inadvertent disclosure of information. Regardless of age, if a participant discloses suicidal ideation or intent, the behavioral health clinician or social worker will be available to assess the level of risk and to help determine the best course of action (e.g. send to the emergency room).

### 8.5 Criteria for Premature Discontinuation

Participants may choose to withdraw themselves from the study at any time. The study is voluntary and the alternative to participating in any phase of the study is not participating.

## 9.0 MONITORING & REPORTING SAFETY EVENTS

Site staff must follow their oversight IRB's procedure for reporting and managing safety events, as well as the ATN CC procedures outlined below and in Chapter 10 of the ATN Manual of Policies and Procedures (MOPP). Safety events are reported using the ATN QNS accessible through the ATN website (<https://www2.cscc.unc.edu/atn/>). All safety events will be reviewed by the study team and reported to NIH.

### 9.1 Study Team Review

Given that this study is a short pilot study of a behavioral intervention with a single arm (a pre-/post study), this study will use study team review for clinical research monitoring (CRM), where the study team consists of the Protocol Team at UC, a NIH representative, and the Coordinating Center (CC) at UNC Chapel Hill. Safety events will be reviewed by the study team on a case-by-case basis at team meetings which will occur at least monthly. The members of the study team and data to be reviewed at the meetings are described below.

Study team members:

- Protocol Chair(s)
- ATN Coordinating Center Investigator
- Protocol Manager
- Project Manager
- NIH Representative

During the study team meetings, data quality and participant safety (e.g., number and type of safety events, recruitment and retention) will be reviewed and the team will determine what actions are necessary, if any. The study team will also previously reported safety events for which new information is available.

The CC will monitor accrual and retention based on reports which they will generate monthly. Reports will include accrual, baseline characteristics, data quality, and completeness. If there are any problems with accrual or retention rates at specific sites, the CC will work with the site to identify operational issues or problems and take appropriate action.

## **9.2 Reportable Safety Events**

There are three types of reportable safety events that require expedited reporting in QNS (within 2 reporting days of site awareness):

1. Adverse events (AEs) deemed to be possibly related or definitely related to the study that are severity grade 3 or higher
2. All serious adverse events (SAEs)
3. Untoward events (UEs) deemed to be possibly related or definitely related to the study that are severity grade 3 or higher

Please note that all community UEs (not graded) and UEs grades 1-2, as well as AEs grades 1-2, do not require expedited reporting. These types of events must be reported within 5 reporting days of site awareness, and are up to the discretion of the site investigator and protocol team as to whether or not they are reportable.

Once entered into QNS and after study team review, safety event reports should be printed and filed with participant records (or with regulatory documents if not related to a specific participant). In addition, study staff must also follow their oversight IRB procedures for reporting and managing safety events.

For more information regarding the definitions of each type of safety event and details on reporting, please refer to the ATN CC MOPP Chapter 10.

## **9.3 Safety Event Reporting Periods**

Safety events must be reported throughout the duration of a study. If the event involves a specific study participant, events must be reported for the duration of that participant's enrollment in the study. After the protocol-defined reporting period ends, only events that study staff become aware of on a passive basis (from publicly available information) should be reported.

The duration of the reporting period for community UEs events begins at project start-up and continues through any professional or lay publication of study findings. If the online reporting system is not available after study closure, electronic reports should be made directly to Program Staff at NICHD.

All potential safety events should be reported as soon as possible after site staff become aware of the event. Events that require expedited reporting (are grade 3 or higher or SAEs of any grade) must be reported within 2 reporting days (see guidance below) of site awareness. Grades 1 & 2 events and all community UEs must be reported within 5 reporting days of site awareness.

Reporting Days:

- A reporting day starts at 12:00 AM (midnight) and ends at 11:59 PM local time.
- A day is counted as a reporting day regardless of the time of day that awareness occurred. The day a site indicates that site personnel became aware of an EAE that meets reporting criteria shall count as day 1 if that day occurs on a reporting day (i.e., Monday through Friday). If that day occurs on a non-reporting day (i.e., Saturday or Sunday), then the next reporting day shall count as day 1.
- Monday through Friday count as reporting days.
- Saturday and Sunday are not considered reporting days.
- Any holiday that occurs on a Monday through Friday counts as a reporting day.

## **10.0 STATISTICAL/ANALYTIC CONSIDERATIONS**

### **10.1 Study Design**

This protocol uses three distinct phases, each with its own study design. Phase I will consist of qualitative research using focus groups of both: (1) the study population (i.e., YMSM and YTW); and (2) employers of the study population. The goal of Phase I is to tailor the intervention, designed to increase employment in an adult population, to the study population.

Phase II and III of the protocol will use a pre-/post design to determine preliminary efficacy of the revised intervention tailored to youth and designed to increase employment. Additional secondary outcomes, and potential mediators and effect modifiers of the intervention, will be considered.

### **10.2 Sample Size and Power Estimates**

Given the exploratory nature of this study and limited access to this population, a power calculation was not performed. A repeated measures design was chosen to reduce the variability in the estimate of the treatment effect, at the expense of having a comparison group. This trade-off was appropriate given the exploratory nature of a pilot study and the limited access to the study population.

### **10.3 Statistical Analysis Plan**

#### **10.3.1 Data Analysis**

The analytic plan is designed to: (1) tailor the adult intervention to youth; (2) assess intervention feasibility, acceptability, and satisfaction; and (3) determine preliminary efficacy of the intervention by comparing pre-/post assessments of employment and sexual risk behaviors.

#### **Phase I**

Data collection, storage, and analysis will take place at the study site (University of Chicago) and will be the responsibility of the Protocol Chair.

Interviews and focus groups will be transcribed and coded by trained qualitative researchers. These transcripts will be coded for patterns and themes that emerge from the data, and these data will be used to inform the revision of the employment intervention that will then be pilot-tested. All focus groups and

key informant interviews will be digitally audio-recorded, transcribed (verbatim), and analyzed using emergent inductive logic data aggregation and analysis in Atlas.ti 7.0. Major emergent themes will be used to create a codebook and two-independent coders will analyze all data separately and compare coding schema for internal reliability (Kappa) (Aim 1). Descriptive statistics will be used to analyze the proportions and central tendencies for all feasibility, acceptability, and satisfaction measures: helpfulness, comprehensibility, quality, content appropriateness, engagement, utility, satisfaction, belief in efficacy, and recommendation to a friend.

Datasets for Phase I will be cleaned, verified and archived, and then entered into SPSS for analyses. All database files will be password-protected and backed up to a secure university server daily.

#### Phase II and III

##### 10.3.1.1 Descriptive statistics

Descriptive statistics will be used to analyze the proportions and central tendencies for participant sociodemographic characteristics collected in the surveys completed by participants in the pilot-tests. We will first generate frequencies, means, and other measures of central tendency as appropriate to describe our sample and outcomes at each of the three time points (T1, T2, T3). Sensitivity analyses will be performed to address extreme outlying variables, including the removal of records with extreme outlying values from analyses.

Changes in primary and secondary outcomes between Baseline (T1) and Follow-Up (T3) will be assessed using paired t-tests for continuous variables and McNemar's test for categorical variables. Other statistical tests that appropriately account for the correlation in the dataset will be considered as needed. All hypothesis testing will be done at an alpha-level of 0.1, given the pilot/exploratory nature of the study.

##### 10.3.1.2 Modeling

The primary goal of the modeling will be to help evaluate what characteristics could be mediators or effect modifiers of the effect of the intervention. Continuous outcomes will be analyzed using linear regression or generalized linear models, discrete outcomes will be analyzed using Poisson regression, and logistic regression will be used for binary and categorical outcomes. Only variables that have a statistically significant univariate relationship with the given outcome, at an alpha-level of 0.2, will be considered as potential mediators or effect modifiers for the effect of the intervention.

Datasets for Phase 2 and 3 will be collected using CDART and cleaned, verified and archived by the ATN CC.

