**Convene a Community Advisory Board (CAB).** Up to a 12-member CAB of YMSM, YTW, youth-serving employment and vocational specialists, LGBT employment training and placement experts, and sexual health educators will be led by [name] and the investigative team. Members of the CAB will meet no less than 20 times over the course of the project to review and interpret qualitative findings into distinct curriculum adaptations. The CAB will be instrumental in providing information on curriculum content, appropriateness, cultural sensitivity and specificity, study methodology, and best methods for enhancing participation, as well providing ongoing feedback and interpretation of data. The CAB will ensure that the adaptations reflect YMSM's and YTW's experience and employment needs (Aim 2).

**Aim 3: Refine, pre-test, and pilot-test the employment intervention.** In order to achieve Aim 3, we will incorporate all qualitative findings and refine the final intervention curriculum modules using additional feedback from the CAB. In addition, the CAB will assist with Phase 2 by pre-testing and providing feedback on Phase 2 data collection instruments.

The adapted employment intervention will first be pre-tested (Baseline, workshops, Post-intervention) with an initial sample of up to 5 participants in order to test the implementation of assessments and workshop activities. Refinement to workshop activities will be considered if activities do not fit within the session time-period or participants do not understand or comprehend the activity.

Next, the intervention pilot-test of the final adapted employment intervention will be completed with a diverse sample of up to 70 YMSM and YTW, ages 16-24, in a single-arm longitudinal pre/post study of the employment intervention to evaluate *feasibility, acceptability, program satisfaction, and preliminary efficacy* using assessments at Baseline (T1), Post-Intervention (T2), and 8 Months Follow-Up (T3).

**Aim 4: Refine and pilot-test the intervention in community-based settings.** In order to achieve Aim 4, we will refine the procedures and intervention so that it may be conducted within community-based settings in order to further test the implementation of assessments and workshop activities in Phase 3.

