## 6.2 Baseline/Enrollment

After informed consent and eligibility has been confirmed, participants will undergo biological specimen collection for HIV/STIs screening and drug testing. Please note that for Phase 3, if a participant has a known positive HIV status they will not undergo HIV testing. Participants will be given an iPad tablet and headphones and asked to complete an ACASI survey. The survey includes items on: sociodemographics, employment variables, HIV risk behavior variables, and potential modifying variables including perceived transgender discrimination scale, job seeking self-efficacy, managing interview, resilience, employment and job search, integrated motivations, internal self-concept, goal internalization, perceived social support, drug use, alcohol use, sexual history, commercial sex work, homelessness, condom intentions, money inventory, and PrEP awareness.

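### The protocol admits mediators and effect modifiers by a univariate p<0.2 screen, but in a single-arm study that screen can show at most predictors of outcome or change

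*Protocol*

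**What the plan says.** Protocol 10.3.1.2 gives the modelling a primary goal, to "help evaluate what characteristics could be mediators or effect modifiers of the effect of the intervention". The entry rule follows: "Only variables that have a statistically significant univariate relationship with the given outcome, at an alpha-level of 0.2". A variable that passes gains the status of a candidate and nothing more. The section gives no interaction term, mediation model, shortlist, adjustment for the outcome's baseline or second-stage criterion. The preceding section sets the level for hypothesis tests: "All hypothesis testing will be done at an alpha-level of 0.1, given the pilot/exploratory nature of the study".

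Protocol 5.0 describes Phase 2 as being conducted "in a single-arm longitudinal pre/post study of the employment intervention", and Phase 3 has the same design. Protocol 10.2 says that repeated measures were chosen "at the expense of having a comparison group" and that "a power calculation was not performed".

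The nearest thing to a candidate list is the account of the baseline survey in Protocol 6.2, which covers "potential modifying variables including perceived transgender discrimination scale, job seeking self-efficacy, managing interview, resilience" and 13 further domains. Job-seeking self-efficacy also appears in section 4.1.3 of both SAPs as a primary outcome, analysed as T3 minus T1.

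Neither SAP mentions the 0.2 screen, mediators or effect modifiers. Sections 5.4 and 5.5 of each plan regression adjusted for named groups of covariates.

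**The concern.** Effect modification means that the effect of the intervention differs with a characteristic. To see it, one needs an estimate of what would have happened without the intervention at each level of that characteristic. Here everyone is assigned the workshops, so an association between a variable and the outcome mixes any variation in effect with ordinary prognosis, time trend, chance and regression to the mean. Mediation also needs a path from the intervention to the mediator, which the screen does not examine.

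The rule can therefore fail in both directions. A variable that only predicts who does well anyway can enter the list. A true modifier can be lost, for example where its link with natural change runs opposite to its link with the effect and the two cancel. Variation in workshop attendance does not supply the missing contrast, because participants choose how much to attend.

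At stake is the label put on the exploratory results. Protocol 2.4 expects the study to lead to an intervention manual for a large multi-site trial, and a list headed as effect modifiers would claim more than the design can show.

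**Working it through.** The documents give no power, error-rate or correlation figure for this analysis, so there is no stated figure to reproduce.

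**Inputs**
- Screening level 0.2, from Protocol 10.3.1.2. Sidedness is not stated; two-sided is assumed.
- Candidates: k = 17 domains, counted in Protocol 6.2. Treating that list as the candidate set is a reading, because 10.3.1.2 does not cite it.
- n = 50, the completion target in Phase 2 SAP 2.3. For Phase 3, up to 40 are enrolled and completers are not stated; 28 is taken as a low value (70% of 40).
- T1-T3 correlation r of the outcome: not in the documents; 0.5 to 0.9 is shown.

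**Step 1: chance passes.** If no candidate is related to the outcome:
- Expected passes per outcome: 17 × 0.2 = 3.4.
- P(at least one), independent candidates: 1 − 0.8^17 = 0.977.
- P(at least one) by simulation at n = 50: 95% with candidates inter-correlated at 0.3, and 88% at 0.5. The expected number stays at 3.4.
- With only 5 independent candidates: 1 − 0.8^5 = 0.67.

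**Step 2: an outcome's own baseline.** Let Y1 and Y3 have equal variance and correlation r. Then cov(Y1, Y3 − Y1) = (r − 1)σ² and var(Y3 − Y1) = 2(1 − r)σ², so

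corr(Y1, Y3 − Y1) = −√((1 − r)/2).

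Adding the same shift to everyone's Y3 leaves this unchanged, so it holds with no effect or with a uniform one. Simulated pass rates for the two-sided correlation test at 0.2, against a nominal 20%:

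| Assumed r | corr(baseline, change) | n = 50 | n = 28 |
|---|---|---|---|
| 0.5 | −0.50 | 99% | 94% |
| 0.7 | −0.39 | 94% | 79% |
| 0.8 | −0.32 | 84% | 66% |
| 0.9 | −0.22 | 62% | 47% |

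**Step 3: correlates of the baseline.** A variable correlated 0.5 with the baseline score, and otherwise unrelated to T3, passes against change in 70% of samples at n = 50 with r = 0.5, and in 54% with r = 0.7.

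**Step 4: real associations.** A true correlation of 0.3 with the outcome passes 81% of the time at n = 50 and 63% at n = 28. The screen admits real associations as well as artefacts, but it cannot say which of the real ones reflect a varying intervention effect.

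**Step 5: does adjusting for T1 cure the artefact?** It depends on how the scores arise. Both cases use n = 50 and no intervention effect.
- If T3 depends on the observed T1 score (r = 0.5), adjustment lowers the pass rate of the Step 3 variable from 69% to 19% at the 0.2 level, which is about nominal.
- If a stable true score is measured with error at both visits (reliability 0.5 to 0.7), a predictor correlated 0.3 to 0.5 with the true score is significant at 0.1 in about 20 to 45% of samples after T1 adjustment, against about 10% with the change score.

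So neither estimate is safe under both models.

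**The case against.** The strongest reply is that little follows from the rule in practice. It is an entry gate; the text speaks of potential modifiers; the work is labelled exploratory; and no later step turns a candidate into a finding. Neither SAP carries the screen, and the SAPs are the detailed plans. All of this stands. A reader might infer that the trial will name false effect modifiers, that its main pre/post results are compromised, or that the list will decide whom the later trial targets. The documents support none of these. The T1-T3 tests do not use the screen, and Protocol 2.4 speaks only of a manual to be tested.

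The candidate set is also an inference. Protocol 6.2 describes survey content, Protocol 6.4 groups self-efficacy with the employment variables, and nothing says outright that baseline self-efficacy would be screened against its own change. The entry rule refers only to the outcome in question, so the regression-to-the-mean figures apply only where that outcome is a change score. The sections on T1-T3 change make that the natural reading but do not compel it. If the T3 level were modelled instead, the screen would pick prognostic variables, which are still not modifiers.

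Finally, the lack of a comparison group is already acknowledged in Protocol 10.2. But accepting that limit for the overall effect estimate does not justify a modelling goal that needs the missing contrast. Exploratory status excuses imprecision, not a label that the design cannot support.

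**Conclusion.** The concern holds for the stated goal and entry rule in Protocol 10.3.1.2. In this design, passing the screen identifies at most a predictor of outcome or change; it is evidence of neither mediation nor effect modification. That conclusion rests on the single-arm design alone and needs no numerical assumption.

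The sizes are conditional. The 3.4 expected chance passes require the 17 listed domains to be the candidates and all to be null; the 98% also requires independence. The 94 to 99% for self-efficacy against its own change requires a change-score outcome, equal variances, n = 50 and an assumed T1-T3 correlation of 0.7 to 0.5; it falls to about 62% at 0.9.

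The consequence is confined to exploratory modelling. It would be too strong to say that the rule selects only noise, since real associations pass too, or that regressing T3 on T1 would remove the artefact. There is also a plain mismatch: the protocol's main modelling goal has no counterpart in either SAP.

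**What to change.** In Protocol 10.3.1.2:

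1. Replace the terms mediators and effect modifiers by exploratory baseline predictors of change, and state that neither mediation nor effect modification can be concluded from this design.
2. Delete the univariate 0.2 screen.
3. Name a short set of baseline variables in advance and report each estimate with a 90% confidence interval, which matches the study's 0.1 level.
4. Do not interpret an outcome's own baseline as a predictor of its change.
5. For other predictors of outcomes that have a T1 value, report both the T1-adjusted and the change-score estimates. T1 adjustment can reduce the regression-to-the-mean artefact but does not reliably remove it when the baseline is measured with error.

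This removes the mismatch with the SAPs, which have no screen and no modifier analysis. A sentence in each SAP naming the chosen variables would complete it. No new data are needed. The cost is a change of wording, a narrower claim and slightly more analysis.
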